2.1. Primary Study Objective

To determine the impact of GC test results on adjuvant treatment decisions of high-risk post-RP patients with undetectable post-op PSA compared to clinical factors alone. Specifically, determine whether higher GC risk increases the likelihood of receiving adjuvant treatment and lower GC risk decreases the likelihood of receiving adjuvant treatment compared to subjects with similar CAPRA-S score who do not have the GC test.

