2.2. Secondary Objectives

1. To determine whether the decision impact of the GC test is of benefit to patients. Specifically, is net benefit of GC use superior to those who do not have the GC test as assessed by decision curve analysis.
2. To determine whether use of the GC test results in decreased likelihood of adjuvant treatment for subjects with high CAPRA-S score (≥ 5) and increased adjuvant treatment for subjects with low CAPRA-S score (< 5). The hypothesis is that there is a non-zero interaction between GC test use and CAPRA-S.
3. To determine whether GC use is associated with earlier use of salvage therapies in CAPRA-S low risk patients and later use of salvage therapy in CAPRA-S high-risk patients.

4. To determine whether use of GC results in improved protection from BCR and metastatic progression.
5. To investigate the impact of GC use on QOL, and whether there is differential QOL impact among CAPRA-S high- and low-risk patients.
6. To determine whether collaborative-wide education and the use of CAPRA-S scores in the control group impacts rates of adjuvant radiotherapy compared to historical controls.

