6.1. FFPE Block Selection/Specimen Acquisition

FFPE (formalin fixed paraffin embedded) tissues from RP prostate tumor sample blocks will be collected from patients in both the GC and UC arms for transcriptome-wide expression analysis.

The FFPE block from the RP that exhibits a) highest Gleason Score, AND b) highest percent tumor involvement will be selected for sampling with at least 60% tumor by surface area. The pathologist will mark the H&E slide that will be used to guide punching. The marked area should preferentially sample tumor with the highest Gleason grade (e.g., in a 4+3 lesion, the pattern 4 component should be enriched in the punch specimen). Two (2) X 1.5 mm in diameter punches will be sampled from the RP FFPE block (e.g., using a tissue microarray core device or a disposable punch tool, to be provided by GenomeDx). Each punch will be placed in a separate microfuge tube and stored at 4°C until shipping.

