6.5. GenomeDx Decipher[®] Testing

GenomeDx will extract and purify RNA from submitted tumor specimens. If the sample fails to yield sufficient RNA (at least 100 ng) GenomeDx will request a duplicate specimen from the submitting physician (preferably from a different FFPE block for that patient). GenomeDx will then generate cDNA, amplify, label and hybridize it to oligonucleotide arrays. The Decipher gene signature tested will remain unchanged throughout the course of the study, such that all patients will undergo the identical assay.

GenomeDx will then perform QC on the raw microarray data. Samples that fail array QC will be re-amplified (provided there is sufficient RNA remaining). If there is insufficient RNA or the 2nd amplification fails, the duplicate sample will be extracted. After generation of the array data and QC analysis, GenomeDx will return (on dry ice) RNA or specimen cores not used for amplification to the pathologist or discard appropriately.

7. Statistical Considerations

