7.1. Statistical Methods Supporting the Primary Objective

The Primary Objective of this study is to determine the impact of GC test result on adjuvant treatment decisions compared to clinical factors alone. This will be evaluated by testing for an effect of GC score in a regression model which adjusts for CAPRA-S risk score. As a cluster-crossover trial, a generalized linear mixed effects model will be used to model the probability of a subject receiving adjuvant treatment within center, in a specific period of the study. Since GC score is a subject-level covariate, an individual-level regression model is utilized rather than a cluster-level aggregated analysis (Campbell 2014, Chapter 6). Specifically, the model to be fit is

$$\text{logit}\left(\frac{\pi_{ijk}}{1-\pi_{ijk}}\right) = \beta_0 + \beta_1 G_i + \beta_2 (G_i * GC_i) + \beta_3 \text{CAPRA-S}_i + \gamma_j + \phi_k$$

where π_{ijk} is the probability of treatment for the i^{th} subject enrolled in the j^{th} cluster (ie: center) during the k^{th} period, G_i is the group to which the subject is enrolled (GC=1, UC=0), CAPRA-S_{*i*} is that subjects' CAPRA-S score (0-12), GC_{*i*} is the GC score (0-1), $\beta_0 \sim N(\mu, \sigma^2)$ and

$\phi_k \sim N(0, \sigma^2)$ are random cluster and period effects, respectively. The null hypothesis $\beta_2 = 0$ will be tested using a Type III test (SAS PROC GLIMMIX) at a 0.05 significance level. 95% confidence intervals using robust variance estimates will also be calculated.

In addition to the model described above, an additional model including a group-by-period interaction term will be fit to ensure that group assignment in a period is not effected by preceding or subsequent periods. For the purposes of this analysis, the period effect will be

considered fixed. This may detect carry-over effects if behaviors or attitudes of physicians within sites persist or change over the course of the study or if changes in patient education materials or their presentation change from one period to the next. Should this interaction term be significant, an alternative analysis utilizing non-consecutive periods may be used.

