Descriptive statistics for various quantities, including raw treatment rates (and 95% confidence intervals) of adjuvant treatment and type of treatment (hormone and radiation) for discrete risk categories for both CAPRA-S (low-risk 0-4, high-risk ≥ 5) and GC (low-risk ≤ 0.45 , high-risk > 0.45) as well as by clinical center and period. Model-based predicted probabilities of treatment will be calculated for various combinations of CAPRA-S and GC high and low risk along with associated confidence intervals.

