7.2. Interim Sample Size Re-Estimation

A confirmation of assumptions underlying the model described in Section 7.1 and the Power and Sample Size calculations in Section 7.4 will be conducted after no fewer than 150 subjects have been enrolled and adjuvant treatment determinations have been made, several parameters will be estimated based on the accumulated data, but no hypothesis testing will be performed and Type I error will be nominally effected (Lake 2002). The following parameters will be estimated and compared to those assumed in Section 7.4, and the impact on the estimated sample size determined through simulation:

- average enrollment by center, including variance of enrollment and enrollment by period
- intra-cluster correlation (ICC)
- overall rate of treatment

Based on the estimated parameters, the number of centers or sample size may be adjusted while maintaining the requisite 80% power. If simulations indicate that a sample size increase of $>20\%$ will be required to provide adequate power to achieve the Primary Objective, the study may be terminated due to futility.

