7.3. Statistical Methods Supporting the Secondary Objectives

All tests will be two sided at a 0.05 significance level. Individuals who are lost to follow-up will be considered censored in time to event analyses. Treatment plans available at the time of drop-out will be considered the final treatment plans.

Secondary Objective 1: To determine whether the net benefit to subjects in the GC arm is superior to the UC arm. This will be determined by directly calculating the net benefit (Vickers and Elkin 2006) across a range of treatment thresholds, Decision Curve Analysis (DCA). DCA is a method for assessing prognostic models that incorporates clinical consequences and the potential probability thresholds at which the likelihood of a given outcome (eg: progression to metastatic disease) may influence the treatment decision of a patient and their physician. For example, one individual may choose treatment if there is a 5% chance of a given outcome while another individual may not be influenced unless the likelihood of that outcome is as high as 10 or 15%. Thus, this methodology allows for how different patients may differentially weigh false negative or false positive results. The calculated net benefit is plotted against threshold

probabilities, and different prediction tools (eg. CAPRA-S and GC) can be compared across these probabilities. If GC is not superior to UC across all thresholds, the region of superiority will be evaluated to determine if it contains a clinically meaningful ratio of harm due to unnecessary treatment versus missed treatment.

Secondary Objective 2: To determine whether use of the GC test result results in decreased likelihood of treatment for CAPRA-S high and increased likelihood of treatment for CAPRA-S low, a modeling approach similar to that of supporting the Primary Objective will be used, but with a GC-by-CAPRA-S interaction term as follows:

$$\text{logit}\left(\frac{\pi_{ijk}}{1-\pi_{ijk}}\right) = \beta_0 + \beta_1 G_i + \beta_2 (G_i * GC_i) + \beta_3 CAPRA-S_i + \beta_4 (G_i * CAPRA_i * GC_i) + \gamma_j + \phi_k$$

where parameters are defined as previously. The test of $H_0: \beta_4 = 0$ will be performed using a Type III test (SAS PROC GLIMMIX). The direction of the interaction will be evaluated graphically with the probability of treatment based on the model and for empirical probabilities using pre-defined GC and CAPRA-S cutoffs.

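### The primary test (β2 = 0) is the GC-score slope among tested patients; the Section 2.1 comparison with untested patients (β1 + β2·g) has no planned test and no stated power

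*Combined protocol and SAP*

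**What the plan says.** Section 2.1 sets a two-direction question. Higher GC risk should increase treatment and lower GC risk should decrease it, "compared to subjects with similar CAPRA-S score who do not have the GC test".

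Section 7.1 turns this into one test: "This will be evaluated by testing for an effect of GC score in a regression model which adjusts for CAPRA-S risk score". The linear predictor contains G, G×GC, CAPRA-S and random site and period effects. G is 1 in the GC arm and 0 in UC, and there is no GC main effect. The null hypothesis is β2 = 0, where β2 multiplies G×GC.

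The same section adds descriptive output: "Model-based predicted probabilities of treatment will be calculated for various combinations of CAPRA-S and GC high and low risk", with confidence intervals. Sections 7.5.1 and 7.5.2 power β2 only and report 83% at 350 subjects; Section 3 gives 550 subjects. Section 7.2 allows re-sizing "while maintaining the requisite 80% power" and does not say to which quantity the 80% applies.

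For Secondary Objective 2, Section 7.3 says that "a modeling approach similar to that of supporting the Primary Objective will be used", and tests β4 on a G×CAPRA-S×GC product. Section 2.2 words the hypothesis differently: "The hypothesis is that there is a non-zero interaction between GC test use and CAPRA-S".

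**The concern.** Every UC patient has G×GC = 0, so UC patients inform β2 only indirectly, through the CAPRA-S, site and period terms. The randomised comparison is carried by β1 together with β2, and only β2 is tested.

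A significant β2 is likely to be reported as meeting Section 2.1. By itself it shows that treatment rises with the score among patients whose score was reported. It does not show that low scorers were treated less than untested patients, or that high scorers were treated more. The 83% can likewise be misread as power for those comparisons.

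**Working it through.** **1. What the model identifies.** At equal CAPRA-S, site and period, the tested-versus-untested log odds ratio at score g is L(g) = β1 + β2·g. Take 0.2 and 0.7 as a low and a high score. They are illustrative; the documents name only the 0.45 cut. Then L(0.7) − L(0.2) = 0.5·β2. If L(0.2) < 0 < L(0.7), β2 must be positive, so a positive β2 is necessary. It is not sufficient: with β1 = 0 and β2 > 0, L(g) ≥ 0 at every score and testing never lowers treatment.

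**2. The plan's own figures.**
- Site ICC with variance 1: 1/(1 + π²/3) = 23.3%, against the stated 23%.
- Table 1: 83% at n = 350 implies a noncentrality of 2.914, or 0.1558·√n. This predicts 77/83/88/94% at n = 300/350/400/500, against 77/83/88/93% stated. At n = 200 and 250 it predicts 60% and 69%, against 47% and 60%.
- The 83% is reachable but cannot be confirmed, because the GC distribution, the intercept and the unit of the GC odds ratio of 1.47 are not given. Reading 1.47 per 0.1 GC, simulated β2 power at n = 350 is 54–74%, 74–88% or 84–96% for a UC high-risk treatment rate of 8%, 15% or 25%. The range within each reflects the assumed GC spread.
- Reading 1.47 per full 0–1 unit gives power of only about 2.5–5%, so the stated 83% points to the per-0.1 reading.

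**3. The contrast under the plan's odds ratios.** Assume 1.47 is per 0.1 and the arm odds ratio of 0.24 is exp(β1). The second is an assumption, because Section 7.5 says only that the fitted model resembled that of 7.1. Then:
- OR(g) = 0.24 × 1.47^(10g)
- OR = 1 at g = 1.427/3.853 = 0.37
- OR(0.2) = 0.52 and OR(0.7) = 3.56

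**4. Power.** The Section 7.1 model was simulated with two-sided Wald tests at 0.05.
- From the documents: site variance 1, a 3% period ICC (variance 0.13), crossover periods, and the Section 7.5.1 enrolment means.
- Assumed: GC mean 0.33–0.43 and SD 0.155–0.267; CAPRA-S mean 4.2 and SD 2.2; correlation 0.35; overall treatment rate 8–30%; 8 or 14 sites; variance components known, which is optimistic.
- Inputs were chosen so that β2 power at n = 350 lies near the stated 83%. The ranges span the settings and repeat runs.

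| Test | n = 350 | n = 550 |
|---|---|---|
| β2 | 82–91% | 96–98% |
| Decrease at GC 0.2 (OR 0.52) | 11–35% | 22–53% |
| Increase at GC 0.7 (OR 3.56) | 66–81% | 85–94% |
| Both directions | 4–30% | 15–50% |

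The choice of score matters. At n = 350, power for a decrease at GC 0.3 is 4–12%, and for an increase at GC 0.6 it is 43–68%.

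**5. β2 when half of Section 2.1 is false.** With β1 = 0, β2 is rejected in 87–97% of trials at n = 350 and in 97% or more at n = 550.

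**6. What the contrast cannot show.** L(g) compares tested patients at score g with UC patients averaged over their unseen scores. Suppose the report changes nothing, but GC predicts treatment beyond CAPRA-S with the same slope in both arms. The documents do not give the size of any such slope.
- At OR 1.47 per 0.1 (an extreme case), at n = 350 the low contrast is significant in 37–53% of trials, the high contrast in 26–64%, and both in 5–36%. Both reach 18–55% at n = 550. β2 is rejected in 79% and 92%.
- At about 1.2 per 0.1, β2 is rejected in 17–43% across n = 350 to 550, and both contrasts in up to about 7% at n = 550.

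**7. Secondary Objective 2.** The Section 7.3 model has no G×CAPRA-S term. Its β4 is a three-way product that is also zero in UC, so the interaction stated in Section 2.2 is not tested.

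**The case against.** The strongest defence is that the comparison is not missing. The planned model yields it, and Section 7.1 promises predicted probabilities with intervals by CAPRA-S and GC risk. That stands. The gap lies in confirmatory testing, stated power and the rule for making claims, and not in estimation.

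A second objection is that β1 + β2·g has a weakness of its own: an unseen association between GC and treatment moves it with no report effect (step 6). That also stands. The contrast answers the literal comparison in Section 2.1 but does not isolate the effect of the report. β2 is exposed to the same association, so this limits what the contrast can show without rescuing β2.

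A third is that the power figures rest on tuned inputs, that they overpredict Table 1 at n = 200 and 250, and that the about 8% in Section 7.5 is for CAPRA-S high-risk patients and not an overall rate. This is fair, and the figures should be read only as ranges.

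Three stronger readings are tempting but not supported:
- A reader might infer that the plan's odds ratios put the tested-versus-untested odds ratio below 1 at every score. That needs 1.47 per full unit, which is incompatible with 83% power.
- A reader might count it as a failure that β2 is not rejected when testing cuts treatment equally at every score. It is not, because Section 2.1 requires an increase at high GC.
- A reader might take 0.37 as the plan's own crossing point. If GC was a main effect in the model fitted to the earlier studies, 0.24 is not exp(β1) and that figure fails.

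**Conclusion.** The concern holds in this form. The primary test concerns the slope among tested patients, and the stated 83% belongs to it. The comparison in Section 2.1 is β1 + β2·g, which is estimable and described but neither tested nor powered. That much follows from the model as written and needs no assumption.

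The size does need assumptions: 1.47 per 0.1, 0.24 as exp(β1), and assumed score distributions and event rates. On those, power for both directions at GC 0.2 and 0.7 is roughly 5–30% at n = 350 and 15–50% at n = 550. The low-GC direction is the weaker one. Confidence is high in the structural point and only moderate at best in the magnitudes.

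The documents do not support a conclusion that the trial cannot address Section 2.1, nor that adding the contrasts would prove that the report caused a change. The mismatch in Secondary Objective 2 is a separate defect with its own remedy.

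**What to change.** Settle the following before outcome data are examined.

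- Keep the model, and keep β2 as the first test at 0.05. Describe β2 alone as an association among tested patients.
- Pre-specify estimates, confidence intervals and tests of β1 + β2·g at one low and one high GC score either side of 0.45. State the multiplicity control, for example β2 as gatekeeper and then the two contrasts. A fixed order needs no alpha split but blocks the second contrast if the first fails, so the order should be justified.
- Require the matching contrast for any statement that treatment was higher or lower than in untested patients, and both contrasts for the two-direction claim.
- State that the 83% in 7.5.2 and the 80% in 7.2 refer to β2. Tying 7.2 to the contrasts instead could trigger its rule on increases above 20%. Give the unit and the fitted model behind 1.47 and 0.24, and report simulated power for the contrasts.
- Do not attribute the contrasts to the report itself unless UC tissue is scored with results withheld, and G×GC is supported in a model with a GC main effect. Section 6.1 says tissue "will be collected from patients in both the GC and UC arms for transcriptome-wide expression analysis" and Section 6.5 says "such that all patients will undergo the identical assay", but neither names a Decipher score for UC. State that this analysis has lower power. With equal information per arm it is that of half the sample: 350/2 = 175 gives below 47% by Table 1, and 550/2 = 275 gives between 60% and 77%. Simulation gave 52–57% and 72–77%.
- Separately, add a G×CAPRA-S term to the Section 7.3 model and test it for Secondary Objective 2.

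The core changes cost SAP wording, estimate statements and a simulation rerun; they need no new data and do not alter alpha or sample size for β2. UC scoring is the only item that may need extra laboratory work. The real cost is disclosing that the low-GC and two-direction claims are likely to be underpowered.

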2.3. Exploratory Objective

1. To determine whether it is possible that use of GC will result in an overall reduced net cost to the healthcare system by avoiding treatment in many patients.

3. Study Design

This is a 4-5 year (up to 2 years enrollment , 3-year follow-up) prospective, cluster-crossover, unblinded, study of 550 subjects from at least fourteen centers of the Michigan Urological Surgery Improvement Collaborative (MUSIC), a physician-led quality improvement consortium comprised of the vast majority of urology practices within the state of Michigan.

According to the cluster-crossover design, each participating MUSIC clinical center within MUSIC will be randomized to either a Genomic Classifier care-based (GC) or Usual-Care-based (UC) strategy for a period of 3 months, during which all enrolled subjects within the center will be provided the assigned strategy. Random assignments will be generated centrally by a study statistician and provided to centers immediately before commencing enrollment in each 3-month period. The randomization will be based on a random block size of either 2 or 4. This will ensure that each center will have two periods of GC and two periods of UC during the enrollment period, maintaining study-wide balance and blinding of assignments in subsequent periods.

If enrolled during the GC period, both subjects and their treating physician will be provided GC (from GenomeDx) and CAPRA-S (from MUSIC-Central) to inform their treatment plan. In the UC periods, only the CAPRA-S results, provided by MUSIC-Central, will be available. Blinding of subjects and treating physicians will not be possible given the nature of the information.

Subjects enrolled to the GC arm will receive MUSIC-led education about the GC test. The pros and cons of the GC test need to be described by an unbiased clinician scientist including the past history of the test (published studies).

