Secondary Objective 3: Time-to salvage therapy initiation will be modeled using a Cox formulation of a Frailty regression model with a similar formulation (ie: main and random effects) to that used for the primary analysis. Kaplan-Meier curves for GC and UC arms will be plotted, as well as for combinations of high- and low-risk GC and CAPRA-S groups.

Secondary Objective 4: Time-to BCR and metastatic progression will be evaluated similarly to the model described for Secondary Objective 3.

Secondary Objective 5: Summary statistics for all QOL instruments and corresponding confidence intervals will be calculated and compared for the GC and UC subjects and shown graphically over time. Validated instruments are used to measure erectile function, urinary function, sexual interest, and sexual satisfaction. Scores for each domain will be scaled with a minimum to maximum range of 0-100. Comparisons between GC and UC subjects will be made at each timepoint (3, 6, 12 and 24 months after surgery) and on each domain and overall score (VAS 0-10), using an ANCOVA analysis including adjustment for time since surgery. Should the assumptions for ANCOVA not be met (strongly skewed data or substantial ceiling or floor effect) a semiparametric ANCOVA model will be used (as in Buja 1989) to adjust for time-from surgery. If the distribution of time-from surgery is similar in the two groups, a Mann-Whitney test for differences will be used to corroborate the ANCOVA model. For this secondary objective, there will be no adjustment for multiple comparisons across domains or time points.

Exploratory Objective: Using a variety of budget models the cost of care for patients in the GC vs. UC arms will be compared out to 3 years from surgery. This will include estimated costs for adjuvant therapy. Differences in total cost, and differential cost per patient (UC vs GC) will be calculated and compared using either standard t-tests if data is normally distributed or appropriate non-parametric test if data is right skewed.

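### The models omit the centre-by-period unit that is randomised; if that unit carries variance, between-arm contrasts, chiefly Objective 4, get standard errors that are too small, while the primary GC-slope test is essentially unaffected

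*Combined protocol and SAP*

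**What the plan says.** - **Randomised unit.** Under Section 3, each centre "will be randomized to either a Genomic Classifier care-based (GC) or Usual-Care-based (UC) strategy for a period of 3 months". On the number of periods it adds: "This will ensure that each center will have two periods of GC and two periods of UC during the enrollment period".
- **Primary model (Section 7.1).** A logistic mixed model with group, group-by-GC-score and CAPRA-S as fixed effects. Its random terms "are random cluster and period effects, respectively". The period term carries no centre index. The hypothesis beta2 = 0 "will be tested using a Type III test (SAS PROC GLIMMIX) at a 0.05 significance level".
- **Robust variance (Section 7.1).** "95% confidence intervals using robust variance estimates will also be calculated". No clustering level or small-sample correction is stated.
- **Carry-over check (Section 7.1).** A further model adds a group-by-period interaction with period fixed: "This may detect carry-over effects if behaviors or attitudes of physicians within sites persist or change over the course of the study".
- **Power simulation (Section 7.5.1).** A site ICC of 23% and a 3% period ICC across sites. No centre-by-period component.
- **Objectives 3 and 4 (Section 7.3).** Salvage is analysed with "a Cox formulation of a Frailty regression model with a similar formulation (ie: main and random effects" of the primary analysis. BCR and metastasis follow the same approach. Robust variance is not mentioned for them. For the secondary objectives generally, "All tests will be two sided at a 0.05 significance level".

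**The concern.** With only a centre effect and a study-wide period effect, two men treated at the same centre in the same quarter are taken to be no more alike than two men at that centre several quarters apart, apart from a shift common to every centre. A staffing change or a new local policy would break that assumption, and Section 7.1 itself expects physician behaviour within sites to change over time. Its group-by-period interaction averages over centres, so it cannot absorb such local variation.

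The arm is constant within a centre-period. Variance at that level therefore goes straight into any comparison of arms, and a model that sets it to zero understates the standard error. At stake is a nominally significant arm difference in BCR, metastasis or salvage timing that reflects which quarters happened to be GC quarters at a few centres.

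**Working it through.** **Inputs.** From the documents: 550 subjects and at least 14 centres (Section 3); four periods per centre; site ICC 23% and period ICC 3% (Section 7.5.1); odds ratios 1.47, 1.15 and 0.24, and about 8% adjuvant treatment among CAPRA-S high-risk men (Section 7.5); site enrolment rates (Section 7.5.1; site 5 is not listed and was taken as 4 per month). Assumed: the centre-period variance, the GC-score distribution (Beta(1.5, 2.2)), 1.47 read as per 0.1 of GC score, and the intercept.

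**Step 1: reproduce the plan's figures.** Centre variance 1 on the logit scale gives ICC = 1/(1 + π²/3) = 23.3%, matching the stated 23%. For 350 subjects, 8 sites and 3 periods, simulated power for beta2 was 72.5%, 82.7% and 88.8% at overall event rates of 7.8%, 9.8% and 13.1%. With 14 sites and 4 periods it was 85.7% at 9.8%. The stated 83% is attainable, at an event rate the documents do not give.

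**Step 2: arm effect under the null, N = 550, 14 centres, 4 periods.** Centre plus centre-period variance is held at 1, with period variance 0.1. The planned centre-plus-period model was fitted, then refitted with a centre-by-period random intercept (300 to 400 trials per row; Monte Carlo error about 1 to 2 points).

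| Event rate | Centre-period variance | SE / true SD | Rejection, planned model | Rejection, added term |
|---|---|---|---|---|
| about 9% | 0 | 0.93 | 5.5% | 3.3% |
| about 9% | 0.2 | 0.89 | 8.3% | 2.8% |
| about 9% | 0.5 | 0.78 | 11.5% | 5.8% |
| about 25% | 0 | 0.98 | 4.3% | 2.0% |
| about 25% | 0.2 | 0.85 | 8.7% | 3.3% |
| about 25% | 0.5 | 0.71 | 15.3% | 4.3% |

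Where the variance is positive, standard errors are 11% to 29% too small. A separate simulation at 8% events, with a centre effect only and centre variance 1, gave 7.3% at 0.2 and 10.8% at 0.4.

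**Step 3: algebraic check.** With m = 550/(14 × 4) = 9.8 per centre-period, the true variance of the arm contrast is proportional to 1 + (m − 1)ρw − mρb, where ρw and ρb are the within- and between-period ICCs. The planned model forces ρb = ρw and uses 1 − ρw.
- ρw = 0.23, ρb/ρw = 0.8: (1 + 8.8 × 0.23 − 9.8 × 0.184)/0.77 = 1.2208/0.77 = 1.585. SE factor √1.585 = 1.26; actual alpha 12.0%.
- ρw = 0.08, same ratio: (1 + 8.8 × 0.08 − 9.8 × 0.064)/0.92 = 1.0768/0.92 = 1.170. SE factor 1.08; actual alpha 7.0%.

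The second line is the fairer one for adjuvant treatment. The 23% is a logit-scale ICC; at 8% events, centre variance 1 corresponds to about 0.08 on the proportion scale.

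**Step 4: time-to-event proxy.** A Cox model stratified by centre (standing in for the centre frailty), with fixed period effects and variances 0, 0.2 and 0.4, rejected 5.0%, 8.6% and 14.8% at 12% events, and 5.0%, 14.4% and 20.8% at 25% events (1,600 to 2,000 trials each). A smaller repeat (600 trials per setting) agreed in direction, with 11.3% rather than 14.8% at 12% events and variance 0.4. The event rates are assumptions.

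**Step 5: what is not affected.** The beta2 test rejected 4.0% to 7.7% under the null, with no trend in the centre-period variance. Its power at N = 350 without and with the extra term was 86.0% and 85.0% (variance 0.2), and 84.3% and 83.0% (variance 0.5). Arm-specific predicted logits had SE/SD of 1.3 to 1.6 and non-coverage of 1% to 4%, so their intervals were not too narrow.

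**Step 6: robust intervals.** Clustered on 14 centres without a small-sample correction, arm-effect intervals in the Step 2 settings missed the true value about 9% to 12% of the time.

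**The case against.** The strongest defence is that the only hypothesis stated in Section 7.1 is beta2 = 0, and it is sound. No test of beta1 is stated and, with GC score uncentred, beta1 is the arm difference at a score of zero rather than an overall arm effect. Objective 2 tests a coefficient driven by subject-level scores, and no distortion of it has been shown. Objective 3 mainly asks about a differential effect by CAPRA-S, and Section 7.3 writes out no null hypothesis for Objectives 3 or 4. All of this stands. It narrows the point to contrasts between arms, with Objective 4 the clearest case.

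The size is also open. It needs a positive variance that the documents do not give. BCR and metastasis are assessed at 3 years, so a quarter-specific local influence may be weaker there than for treatment decisions near enrolment. The planned frailty model itself was not simulated; Step 4 is a proxy. These objections limit the certainty, but they do not justify fixing the variance at zero without comment.

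Finally, the plan does provide robust intervals. That would answer the point only if the clustering level and correction were stated and suitable. Neither is stated, the centre-clustered version failed in simulation, and nothing extends them to Objectives 3 and 4.

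**Conclusion.** The omission is on the page, and its consequence is conditional. If outcomes vary between periods within a centre, between-arm contrasts have standard errors that are too small. With an assumed logit-scale centre-period variance of 0.2 to 0.5, a nominal 5% arm test rejects about 7% to 15% of the time; at zero it is near nominal. The survival proxy points the same way, but its size rests on assumed event rates.

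A reader might infer that the primary result or the 83% power is compromised, or that the intervals for predicted treatment probabilities are too narrow. The calculations do not support either reading. Nor should the stated 23% be used as a proportion-scale ICC: with 8% events that overstates the inflation (12.0% rather than 7.0% in Step 3). This is a cheap improvement to secondary inference, not a flaw in the primary analysis.

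**What to change.** Add a centre-by-period frailty to the Objective 3 and 4 models, and a centre-by-period random intercept to the Section 7.1 model for any between-arm contrast reported from it. State in advance that the term is dropped only if its variance is estimated as zero. For the robust intervals, state the clustering level and the small-sample correction, and say whether they apply to Objectives 3 and 4.

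The cost is one random term per model and about one point of power for beta2 if the term is also used there. Arm intervals will be somewhat wider and may be slightly conservative: rejection after the fix was 2.0% to 3.3% at variance 0 or 0.2. Zero-variance estimates or convergence trouble should be expected at times, because data per cell are sparse. If 8% of 550 are treated, that is 44 events over 14 × 4 = 56 centre-periods, or about 0.8 per cell.
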